In this pragmatic emulation of a stratified, randomised, open-label, superiority trial, adults referred to secondary care with various shoulder diagnoses and medical imagine verified pathology were initially allocated into either Surgery group, or the Non-Surgical Treatment group with an expected allocation ratio of 1:15. The primary endpoint in the intention-to-treat population was PASS assessed one year from allocation of treatment. Secondary endpoints was assessed also at 3 and 6 months after allocation of treatment. We will analyse observational data from the prognostic Vejle Hospital Shoulder Cohort (VHS Cohort), initiated to evaluate prognostic factors for consistent pain 1 year after diagnosis, using a “causal inference framework”, in an attempt to emulate a randomised target trial, stratified per diagnostic group defined as 1) Degenerative; 2) Traumatic injury; 3) Non-traumatic instability/luxation; 4) Non-specific pain, based upon ICD-10 diagnosis and traumatic/non-traumatic anamnesis (Illustration 1), that would answer the question whether more patients referred for surgery based on a surgeon’s clinical evaluation will reach a satisfactory outcome, when compared to patients not referred for surgery. Thus, causal inference from these observational data needs to be evaluated with respect to how well they emulate a particular target trial that is not feasible/ethical to perform.

[figure not shown]

Illustration 1: Diagnostic grouping based on ICD-10 diagnoses.

The statistical analysis plan (SAP) is reported in accordance with the “Guidelines for the Content of Statistical Analysis Plans in Clinical Trials”.²⁴ Reporting of the trial will follow the “Consolidated Standards of Reporting Trials” (CONSORT).^{25 26}

The trial was registered at Clinicaltrials.gov (NCT04686435) in 12/2020. First patient was enrolled in January 2021. Last patient last follow-up was January 2025. The trial has been evaluated and approved by The Regional Committees on Health Research Ethics for Southern Denmark (Project.ID: S-20202000-16) and the Danish Data Protection Agency (journal no: 20/12316).

Group allocation

Allocation to surgery or non-surgical treatment is based on the clinician’s initial overall judgment, taking into account patient history, clinical examination, imaging findings, patient expectations, relevant clinical guidelines and shared decision making. This real-world allocation process was analytically emulated to reflect a trial-like comparison.

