Sample size and power considerations

The sample size calculation applies jointly to both primary efficacy objectives. A power analysis for comparing two proportions using Pearson’s chi-square test indicated that, with a 1:15 allocation ratio between groups, a total sample size of 992 would provide 92% power to detect a 20 percentage point absolute difference (0.80 vs. 0.60) at a two-sided significance level of 5% ($\alpha = 0.05$). The calculation employed a normal approximation to the binomial distribution under the null hypothesis of no difference in proportions. For practical and operational considerations, the sample size was rounded up to 1000 participants to ensure sufficient power and account for potential deviations.

Framework

Both primary and secondary outcomes are analysed within a superiority framework; surgical interventions are favourable compared to non-surgical interventions.

Statistical interim analysis and stopping guidance

No statistical interim analysis is planned on the primary endpoint.

Timing of final analysis

Data extraction and analysis for the between-group comparison (Surgical vs. Non-Surgical) for the primary endpoint (1 year follow-up) is planned to be performed after making this SAP public available. The main publication of the trial will be prepared when these data have been received and cleaned (anticipated by September 2025).

Timing of outcome assessments

The overview of trial procedures and time-point of each outcome assessment is presented in the **Illustration 2** “Timeline for recruitment and follow-up” and **Box 1** “Outcomes and Covariates – Timepoint of assessment”. The Treatment allocation date (Surgical or Non-surgical) is used to calculate 3 months, 6 months and 1 year follow-up time points.

[figure not shown]

Illustration 2: Timeline for recruitment and follow-up. -t₂: 2-4 days prior to medical examination; -t₁=Day of medical examination; t₀=Allocation; t₁= 3 months; t₂= 6 months; t₃= 1 year.

STATISTICAL PRINCIPLES

Confidence intervals and p-values

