All statistical tests and 95% confidence intervals (95%CIs) will be two-sided and *p-value* < 0.05 will be considered statistically significant for the primary and co-primary endpoint. Groups will be considered comparable if the two-sided 95% confidence interval for the odds ratio comparing Shoulder Surgery with Nonoperative Treatment, for both the primary and co-primary endpoint, lies entirely within the range of 0.80 to 1.25.²⁷ In the secondary outcomes Quick-DASH and VAS, a 95% confidence interval excluding a difference greater than 10 Quick-DASH points or 10 points on VAS between the two groups will be interpreted as indicating absence of a minimal clinically important difference (i.e. possible equivalence).

To address multiplicity, a gatekeeping procedure will be applied to both the primary objectives and the key secondary objectives to determine which will be used in the interpretation of the study results. While all outcomes will be analysed and presented, only those passing the gatekeeping procedure will be considered for inferential conclusions. The gatekeeping procedure follows a hierarchical approach in the prioritised order listed below. Statistical testing will proceed sequentially until an analysis fails to show a statistically significant difference (*p* < 0.05), or until all analyses have been completed.

If a test does not meet the specified statistical significance threshold, no further claims will be made for subsequent outcomes in the hierarchy:

- 1) PASS
- 2) Quick-DASH MIC
- 3) GPE
- 4) Quick-DASH

- 5) Maximum Pain
- 6) Pain in activity
- 7) Pain at rest
- 8) Shoulder related sleep disturbance

Adherence and protocol deviations

Adherence to the surgical intervention is assessed by the percentage of patients being referred to surgery at the initial clinical evaluation, and the actual number of these patients having a record of the surgery was performed in the REDCap database, including date and type of surgery performed: adherence% = (Number of patients with a surgical record in REDCap database/ number of patients referred for surgery at first medical examination) x 100.

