Results will be reported as means and standard deviations unless otherwise indicated. PASS: Patient acceptable Symptom State; Quick DASH MIC: Short version of the Disability of the Arm, Shoulder and Hand Questionnaire (Quick-DASH) criteria for Minimal Important Change (41% change); GPE: Global Perceived Effect; Quick-DASH: The short version of the Disability of the Arm, Shoulder and Hand Questionnaire (Quick-DASH); VAS: Visual Analog Scale; WHO-5: The World Health Organization-Five Well-Being Index³⁸; EQ-VAS: European Quality of life – Visual Analog Scale³⁹; PSEQ(4): Pain Self-Efficacy Questionnaire – 4 item⁴⁰; TSK-13: Tampa Scale of Kinesiophobia 13 item⁴¹; UCLA-as: University of California Los Angeles Activity Scale⁴²; *Metabolic syndrome defined as 2 or more positive factors out of: 1) Medication due to hypertension; 2) Medication due to Triglycerides/HDL; 3) Insulin resistance; 4) Waist-To-Height ratio >0.5.

Analysis methods

All descriptive statistics and statistical analysis will be reported in accordance with the recommendations of the *“Enhancing the Quality and Transparency Of health Research”* (EQUATOR) network⁴³ and the CONSORT statement.⁴⁴ Visual inspection (QQ-plot, histograms, and scatterplots) of the standardised residuals from the statistical model will be used to assess the assumption of normality and homogeneity of variances. Following the flow diagram (Figure 1), which outlines the population included in the intention-to-infer analysis, baseline characteristics will be summarised by study group (Table 1).⁴⁵ This table will include demographic variables, relevant medical history, and other baseline factors potentially associated with exposure and the outcomes of interest.²⁷

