The primary analyses will be based on the Intention to Treat (ITT) population. Categorical endpoints (e.g., the proportion achieving PASS/Quick-DASH MIC after 1 year) will be analysed using logistic regression, with treatment group and stratification factors as covariates, based on the IPW data provided initially. The primary estimand will be the odds ratio (OR) with 95% confidence intervals (CIs) derived from the fully adjusted logistic regression model. The main analysis will use inverse probability weighting, with further adjustment for stratification variables. The OR will represent the treatment effect, with CIs providing the range within which the true treatment effect is expected to lie with 95% certainty. A p-value will be reported to assess the statistical significance of the treatment effect, testing the null hypothesis of no difference between groups. An OR >1 indicates higher odds of achieving the PASS/Quick-DASH MIC outcome with surgical treatment, while an OR <1 indicates lower odds. For secondary objectives, categorical outcomes will be analysed using the same approach as the primary endpoints, while continuous outcomes will be analysed as change from baseline using repeated-measures mixed-effects linear models. Patient identification number will be included as a random effect. Fixed effect factors will include baseline score, treatment group (Shoulder Surgery vs Nonoperative Treatment), time point (baseline, 3, 6, and 12 months), stabilised inverse probability of treatment weighting (sIPTW), and treatment-by-time interactions.

Sensitivity analysis will be performed with the purpose to test the robustness of the primary analyses, based on the per-protocol population, if $>5\%$ of the total number of patients in one treatment group are major protocol violators. The per-protocol analysis set will include: 1) patients who in the surgical group were 'allocated (initial clinical decision at first medical examination) to receive surgery, and have a record of the surgery was performed in the REDCap database, including date and type of surgery performed, 2) patient who in the non-surgical group were allocated (initial clinical decision at first medical examination) to receive non-surgical treatment and a minimum of 1 record, in the REDCap database, of receiving non-surgical intervention after the initial clinical examination as well as no record of surgery performed.

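### The mixed model for the five continuous key secondary endpoints has a patient random effect as its only covariance term, which at the planned 1:15 split leaves the 1-year intervals unprotected if spread differs by arm or visit

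*SAP*

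**What the plan says.** All of this is in the SAP.

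- **Analysis methods, model:** "continuous outcomes will be analysed as change from baseline using repeated-measures mixed-effects linear models". The covariance side of the model is one sentence: "Patient identification number will be included as a random effect". The fixed effects are baseline score, treatment group, "time point (baseline, 3, 6, and 12 months), stabilised inverse probability of treatment weighting (sIPTW), and treatment-by-time interactions". No residual covariance structure, no variance by arm or visit and no robust standard error is named.
- **Analysis methods, checks:** plots of standardised residuals "will be used to assess the assumption of normality and homogeneity of variances". Nothing is said about what follows if the plots look bad.
- **Trial design:** "expected allocation ratio of 1:15". **Sample size and power considerations:** "with a 1:15 allocation ratio between groups, a total sample size of 992 would provide 92% power", that is 62 surgical and 930 non-surgical patients.
- **Confidence intervals and p-values:** the five continuous endpoints are steps 4 to 8 of the testing hierarchy, each at 5%. For Quick-DASH and the VAS scores, a 95% interval that rules out a difference above 10 points "will be interpreted as indicating absence of a minimal clinically important difference".
- **Table 2 footnote:** names repeated measures mixed models for these endpoints but gives no covariance structure.

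**The concern.** A linear mixed model with a patient random effect and nothing else on the covariance side is a random-intercept model. It has one variance for both arms and all visits, and one correlation between any two visits. With equal arms, a wrong assumption about the arms does little harm to the standard error of a contrast. With a 1:15 split it can do a good deal, because the variance estimate is dominated by one arm and the uncertainty of the contrast by the other.

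If surgical patients vary more at 1 year than non-surgical patients, the intervals are too narrow: type I error rises, and a 10-point difference is ruled out too easily. If they vary less, the intervals are too wide and power is lost. A change in spread from 3 to 12 months is a second route to the same problem, because the 1-year contrast then borrows a variance averaged over visits.

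The Missing data section relies on this model for valid inference when data are missing at random. That also presupposes an adequate covariance. No additional analyses are planned that would show a problem.

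**Working it through.** **Inputs.** From the SAP: N = 992 at 1:15, so n1 = 992/16 = 62 and n0 = 930; two-sided 5%; a 10-point margin. Assumed, because the SAP gives no SD: surgical/non-surgical SD ratio r from 0.8 to 1.5; visit SDs 18, 20, 22; a non-surgical SD of 20 where a result in points is wanted. The arm ratios below do not depend on the 20.

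**1. The plan's own figure.** Two proportions, 0.80 v 0.60, 62 v 930, chi-square normal approximation. Pooled proportion = (62×0.80 + 930×0.60)/992 = 0.6125; power = 0.920. The stated 92% is reproduced, which confirms the 62 v 930 split.

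**2. Where the two quantities come from.** Share of the pooled variance estimate from the non-surgical arm: 930/992 = 93.8%. Share of the variance of the contrast from the surgical arm at equal SDs: (1/62)/(1/62 + 1/930) = 93.8%.

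**3. Arm effect.** With the non-surgical SD set to 1:
- model SE² = [(62r² + 930)/992] × (1/62 + 1/930)
- true SE² = r²/62 + 1/930
- type I error = 2[1 − Φ(1.96/q)], where q = true SE/model SE

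| r | pooled variance | model SE | true SE | q | type I error |
|---|---|---|---|---|---|
| 0.8 | 0.978 | 0.1297 | 0.1068 | 0.82 | 1.7% |
| 1 | 1.000 | 0.1312 | 0.1312 | 1.00 | 5.0% |
| 1.25 | 1.035 | 0.1334 | 0.1621 | 1.21 | 10.7% |
| 1.5 | 1.078 | 0.1362 | 0.1933 | 1.42 | 16.7% |

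At 496 v 496, q is 1.00 for every r, so this part is due to the unequal split.

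**4. In points, at a non-surgical SD of 20.** The model's 95% half-width is about 5.1, 5.1, 5.2 and 5.3 for r = 0.8, 1, 1.25 and 1.5. The correct half-width is 4.2, 5.1, 6.4 and 7.6. If the true difference were exactly 10 points, the chance that the interval lies wholly inside the margin would be 1 − Φ(1.96/q): 2.5% nominally, 5.3% at r = 1.25 and 8.4% at r = 1.5.

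**5. Visit effect, equal arms.** Average variance = (324 + 400 + 484)/3 = 402.7. q = √(484/402.7) = 1.10; type I error 7.4%. The sample sizes cancel, so this holds at any allocation ratio.

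**6. Offsetting.** At r = 0.9 the arm part is 0.912. Combined with step 5: 0.912 × 1.096 = 1.00, so the interval is right.

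**7. Checks.** A 6,000-run simulation of the random-intercept analysis on three post-baseline visits gave coverage of 98.4%, 95.5%, 89.0% and 82.6% at r = 0.8, 1, 1.25 and 1.5. Arm-specific 1-year variances gave 94.9%, 95.5%, 94.8% and 95.2%. REML fits of the mixed model gave model/true SE of 1.21, 1.00, 0.83 and 0.70, in agreement with step 3.

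**8. The listed baseline time point.** Steps 3 to 7 use post-baseline visits only. The SAP also lists baseline as a time point, where change is zero for everyone, so one variance over all listed visits cannot hold. With that row kept and equal arms, REML fits gave model/true SE of 0.89 and coverage of about 92%.

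**The case against.** Several objections have force.

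- **The SAP never says there is one variance.** True. A patient random effect can coexist with visit- or arm-specific residual variances. A reader might infer that the plan expressly assumes equal variances in this model; it does not. But no such term is specified, and the SAP itself treats homogeneity as an assumption to be checked. An analyst who follows the text fits the pooled model.
- **The assumption is checked.** Also true, by plots. What stands is that no action follows. With about 6% of residuals from surgical patients, a pooled plot may not show a difference between arms.
- **Unequal spread is not shown.** A reader might infer that equal spread is implausible because the surgical arm mixes diagnoses and procedures. The documents do not support that. The non-surgical arm covers the same diagnostic groups, counts any single recorded non-surgical treatment as adherence, and allows for crossovers to surgery. No SD is given, so neither the direction nor the size is known.
- **The 1:15 split is not to blame for everything.** Correct. Only the arm part disappears at 1:1; the visit part remains.
- **The figures are for complete, unweighted data and the planned split.** Correct. They show sensitivity and do not predict the result.
- **The reach is limited.** PASS, Quick-DASH MIC and GPE use logistic regression and are untouched. Under the hierarchy, the p-values of items 4 to 8 support claims only if the first three tests succeed.

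**Conclusion.** The concern holds as a weakness in pre-specification that is cheap to remove. It is not a demonstrated error in a result. The written covariance pools over arms and visits, and the planned 1:15 split makes the 1-year intervals sensitive to that choice.

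Over assumed SD ratios of 0.8 to 1.5, type I error runs from 1.7% to 16.7%. Rising visit SDs alone give 7.4% under the assumed 18, 20, 22. These figures rest on assumed spreads, on 62 v 930 being close to the observed split, and on complete, unweighted post-baseline data.

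It would go too far to say that the intervals are wrong whenever the arms differ: arm and visit effects can cancel, as step 6 shows. The finding should be acted on before analysis, but it does not touch the primary or co-primary conclusions.

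**What to change.** In Analysis methods, replace the patient random effect for the continuous endpoints with an unstructured covariance over the 3, 6 and 12 month visits, estimated separately by treatment group. In SAS, which the plan already names, this is a REPEATED statement with TYPE=UN and GROUP=treatment. Add the same statement to the Table 2 footnote, which at present names no covariance.

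State the fallback in advance: if the model does not converge, use a common unstructured covariance with a patient-clustered sandwich variance and a small-sample correction. Keeping the fallback unstructured matters. A sandwich variance repairs the standard errors only, and with data missing at random a poor working covariance can also bias the estimate.

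The cost is a sentence or two in the SAP and a line of code. The model has 6 covariance parameters per arm, 12 in all, in place of 2. Intervals widen if the surgical arm is more variable; if the spreads are equal, little is lost. The SAP places data extraction and analysis after its own publication, so the choice is best fixed before then and not after residuals have been seen.

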Pain intensity in the affected shoulder over the past 7 days, assessed separately in three specific contexts:

- Maximum pain experienced
- Pain during physical activity
- Pain at rest

Endpoint:

Each pain domain is measured on a 100 mm visual analogue scale (VAS) anchored with 0 = “No pain” and 100 = “Worst pain imaginable,” as recommended by the OARSI.³⁶ The key secondary endpoint is the between-group difference in change from allocation to 1 year follow-up. Additional measurements will be collected at 3 and 6 months.

4. Shoulder-Related Sleep Disturbance

Outcome:

Degree of sleep disturbance attributed to shoulder symptoms in the past 7 days.

Endpoint:

Measured using a 100 mm VAS, anchored with 0 = “Not disturbed” and 100 = “Extremely disturbed.” The key secondary endpoint is the between-group difference in change from allocation to 1 year follow-up, with additional measurements at 3 and 6 months.

Covariates for development of propensity score

To account for potential confounding and to improve comparability between the surgical and non-surgical treatment cohorts, propensity score adjustment will be applied. The propensity

score will be estimated as the conditional probability of receiving surgical treatment, given a set of baseline covariates measured prior to treatment allocation.

Covariates are selected based on clinical relevance and their potential association with both treatment assignment and outcomes. These include patient-reported measures of general health, health-related quality of life, fear-avoidance beliefs, treatment expectations, and physical activity levels, as well as sociodemographic characteristics (e.g., age, sex, education), lifestyle factors (e.g., smoking, BMI), and clinical assessments including imaging and physical examination findings.

All covariates used in the propensity score model were collected prior to referral to either surgical or non-surgical treatment pathways. The full list of covariates and the timing of their assessment, along with the timing of primary and secondary outcome measurements, is detailed in Box 1.

Box 1: Outcome and Covariates – Timepoint of assessment.

	Timepoint of assessment			
	Baseline	3 months	6 months	1 year
Outcome measures				
Primary outcome				
PASS, no. (%)				X
Quick-DASH MIC, no. (%)				x
Key Secondary Outcomes				
GPE - Overall shoulder problems - no. (%)				X
Quick-DASH - 0-100	X	X	X	X
VAS shoulder pain 'Maximum' - 0-100	X	X	X	X
VAS shoulder pain 'Activity' - 0-100	X	X	X	X

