Range of motion – Active Elevation – degrees	X			
Range of motion – Active External rotation – degrees	X			
Range of motion – Active internal rotation – degrees	X			
Range of motion – Passive Elevation – degrees	X			
Range of motion – Passive External rotation – degrees	X			
Abnormal Isometric strength in elevation, no. (%)	X			
Abnormal Isometric strength in internal rotation, no. (%)	X			
Abnormal Isometric strength in external rotation, no. (%)	X			
Major symptoms	x			
- None, no. (%)				
- Pain, no. (%)				
- Stiffness, no. (%)				
- Instability, no. (%)				
- Decreased strength, no. (%)				
Atrophy of one or more of shoulder muscles, no. (%)	X			
Abnormal Scapula placement, no. (%)	X			
Palpation tenderness of shoulder girdle	X			
- Acromion Clavicular joint, no. (%)				
- Biceps tendon, no. (%)				
- Other, no. (%)				
- Missing, no. (%)				
Ultrasound measures (Acromion Clavicular joint)	X			
- Normal, no. (%)				
- Osteoarrose (Narrowed joint space OR osteophyte), no. (%)				
- Hypertrophy of capsule, no. (%)				
- Luxation, no. (%)				
- Missing, no. (%)				
Ultrasound measures - Structural changes in Rotator cuff, no. (%)	X			
Ultrasound measures (Rotator cuff ruptures)	x			
- Normal, no. (%)				
- Partial, no. (%)				
- Complete, no. (%)				
- Missing, no. (%)				
Ultrasound measures - structural changes in m. Biceps tendon, no. (%)	x			
Ultrasound measures – Inflammation of Bursae, no. (%)	x			

Ultrasound measures - Clinically relevant Calcification, no. (%)				
Radiographic	X			
- Acromion Clavicular joint arthrosis, no. (%)				
- Gleno-Humeral-joint arthrosis, no. (%)				
- Acromion deformations, no. (%)				
- Other, no. (%)				
- Missing, no. (%)				
3 out of 5 positive Clinical test (Hawkins; Neer's; Full can; Empty Can; Resisted ext. rotation), no. (%)	X			
Patient reported outcome measure (PROM)				
WHO-5 - 0-100	X			
EQ VAS - 0-100	X			
PSEQ(4) - DK - 0-24	X			
TSK-13 - 0-52	X			
UCLA-as - 1-10	x			

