Morphine or opioids — no. (%)

Other — no. (%)

Diagnostic group

Degenerative — no. (%)

Non-Specific shoulder pain — no. (%)

Non-traumatic instability/luxation — no. (%)

Traumatic injury — no. (%)

Quick-DASH score‡ — 0 to 100

VAS Shoulder pain Maximum§ — 0 to 100

VAS Shoulder pain Activity§ — 0 to 100

VAS Shoulder pain Rest§ — 0 to 100

VAS Shoulder related sleep

Disturbance§ — 0 to 100

* Plus-minus values are mean \pm SD unless otherwise indicated.† The Danish Health Authority guideline recommends alcohol consumption lower than 7 units per week for females and 14 units per week for males to have a low risk of developing diseases.⁴⁸

‡ The short version of the Disability of the Arm, Shoulder and Hand Questionnaire (Quick-DASH) ranges from 0 to 100, with higher scores indicating worse disease status.

§ Visual Analog Scale (VAS) ranges from 0 to 100, with higher scores indicating worse status.

Table 2. Primary and Key Secondary Outcomes at 1 year in the Intention-to-Treat Population.*

VARIABLE	SURGICAL GROUP	NON-SURGICAL GROUP		BETWEEN GROUP	
		OR (95%CI)		Crude	Adj.
PRIMARY OUTCOME					
PASS - no. (%)					
QUICK-DASH MIC - no. (%)					
KEY SECONDARY OUTCOME					
GPE - OVERALL SHOULDER PROBLEMS - no. (%)					

	Mean change from baseline	SE	Mean change from baseline	SE	LSMean difference (95% CI)	
					Adj.	p-value
Quick-DASH - 0 to 100						
VAS SHOULDER PAIN MAXIMUM - 0 to 100						
VAS SHOULDER PAIN ACTIVITY - 0 to 100						
VAS SHOULDER PAIN REST - 0 to 100						
VAS SLEEP DISTURBANCE - 0 to 100						

PASS: Patient Acceptable Symptom State; GPE: Global Perceived Effect; Quick-DASH: Short form of Disability of the Arm, Shoulder and Hand questionnaire; VAS: Visual Analog Scale. * All analyses will be based on the ITT population: For dichotomous outcomes, logistic regression will be applied, with treatment group and stratification factors as covariates, based on the IPW data (missing data at 1 year from allocation will be addressed through non-responder imputation); The primary estimate will be the odds ratio (OR) with 95% confidence intervals (CIs) derived from the logistic regression model. For continuous outcomes, repeated measures linear mixed effects models (with no imputation for missing data) will be applied; Estimates are mean change from baseline and standard deviations with difference between groups reported with 95% confidence intervals.

Figures:

[figure not shown]

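### The mixed models for the five continuous key secondary outcomes and the propensity covariate list omit the diagnostic group on which the emulated trial is declared stratified

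*SAP*

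**What the plan says.** - **Trial design.** The target trial is "stratified per diagnostic group defined as 1) Degenerative; 2) Traumatic injury; 3) Non-traumatic instability/luxation; 4) Non-specific pain", with the grouping "based upon ICD-10 diagnosis and traumatic/non-traumatic anamnesis".
- **Covariates for development of propensity score.** Box 1 is said to give "The full list of covariates and the timing of their assessment". Box 1 has rows for injury history, major symptoms (instability among them), ultrasound and radiographic findings. It has none for diagnostic group or ICD-10 diagnosis.
- **Analysis methods, binary endpoints.** These "will be analysed using logistic regression, with treatment group and stratification factors as covariates, based on the IPW data provided initially". GPE follows the same approach.
- **Analysis methods, continuous endpoints.** "Fixed effect factors will include baseline score, treatment group (Shoulder Surgery vs Nonoperative Treatment), time point (baseline, 3, 6, and 12 months"), followed by the stabilised weight and the treatment-by-time interaction, with patient as random effect.
- **Table 2 footnote.** For dichotomous outcomes, "logistic regression will be applied, with treatment group and stratification factors as covariates". The clause on continuous outcomes names no stratification factor.
- **Table 1.** Diagnostic group is a baseline row, in a table that has a standardised-difference column.

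**The concern.** By the SAP's own account, diagnosis is made at the first medical examination, which is also where allocation is decided. Its background section says that emulation needs data on the prognostic factors that go with treatment decisions. Having chosen diagnosis as the stratifier, the plan uses it in the outcome models for three endpoints and leaves it out for five.

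At stake are the contrasts for Quick-DASH, the three pain scores and sleep disturbance. If the arms still differ in diagnostic mix after the planned adjustment, and diagnoses differ in their one-year course, part of each contrast reflects diagnosis rather than surgery. These intervals are read in two ways: for superiority within the hierarchy, and against a 10-point bound for possible equivalence. A shift in either direction could therefore affect interpretation.

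**Working it through.** **Where diagnostic group enters**

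| Place in the SAP | Items 1–3 (PASS, Quick-DASH MIC, GPE) | Items 4–8 (Quick-DASH, three pain scores, sleep) |
|---|---|---|
| Propensity covariates (Box 1) | not listed | not listed |
| Outcome model (Analysis methods) | stratification factors included | not in the fixed-effect list |
| Table 2 footnote | stratification factors named | not named |

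Items 4 to 8 are exactly the outcomes analysed by the mixed models, so the gap coincides with that part of the hierarchy. The SAP gives no figure on this point to reproduce. Its stated power concerns the binary endpoints.

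**Illustration of size.** The SAP gives no surgery rate or outcome by diagnostic group, so all inputs below are assumptions. The true effect is set to zero, and a negative difference is a spurious benefit to surgery. Group order is degenerative, traumatic, non-traumatic instability, non-specific.

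- Group shares s: 0.60, 0.15, 0.10, 0.15.
- Strong scenario: surgery probability p = 0.05, 0.16, 0.10, 0.01; mean Quick-DASH change m = −12, −20, −18, −8.
- Mild scenario: p = 0.06, 0.10, 0.08, 0.02; m = −14, −18, −16, −10.

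*Crude difference* = Σspm/Σsp − Σs(1−p)m/Σs(1−p).

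- Strong: −1.032/0.0655 − (−12.168/0.9345) = −15.756 + 13.021, about −2.7.
- Mild: −0.932/0.062 − (−13.268/0.938) = −15.032 + 14.145, about −0.9.

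*Weighted on imperfect proxies only.* Let x be a traumatic-history indicator and an instability indicator. The score is e(x) = Σ s·P(x|group)·p / Σ s·P(x|group). Surgical patients are weighted by 1/e and the others by 1/(1−e); the stabilising constants cancel. Spurious benefit, in points:

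| Assumed proxy accuracy (sensitivity / false-positive rate) | Strong | Mild |
|---|---|---|
| Trauma exact; instability 80% / 5% | about 0.8 | about 0.45 |
| Both 90% / 10% | 1.5 to 1.6 | about 0.6 |
| Both 70% / 20% | about 2.3 | about 0.8 |
| Both 60% / 20% | about 2.45 | about 0.83 |
| Diagnostic group itself in the score | 0 | 0 |

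The proxy rows move by under 0.1 points with the functional form of the score.

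*Cruder check.* For one omitted group, bias is about (residual difference in its weighted share) × (gap in mean change). Assumed share differences of 0.05 to 0.30 and gaps of 5 to 15 points give 0.05 × 5 = 0.25 up to 0.30 × 15 = 4.5 points.

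**Limit of the illustration.** It compares weighted mean changes. The planned model has repeated measures and baseline score, and it lists the stabilised weight as a fixed effect. These figures show an order of magnitude and are not the bias of the planned analysis.

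**The case against.** The case on the other side has real content.

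- **Box 1 covers part of the group.** Injury history is one of its two defining components, and instability, cuff-rupture and radiographic rows also reflect diagnosis. This stands as a limit on size. It does not guarantee balance on an ICD-10-based grouping. Because the mixed models list the weight as a fixed effect, which is a separate matter, even the indirect balancing is less assured for these outcomes.
- **The stratifier is not wholly unused.** Analysis methods ends with a rule for subgroup analyses in balanced diagnostic groups if the stratification proves imbalanced, and it is not confined to binary endpoints. A reader might infer that diagnostic group plays no part at all for items 4 to 8; that goes too far. The rule still does not adjust the main contrasts.
- **The fixed-effect list may not be exhaustive, and the adjustment for stratification variables might be meant generally.** That adjustment sits in the odds-ratio text, the continuous outcomes then get their own list, and the Table 2 footnote repeats the split. If general adjustment was intended, the wording still needs correcting.
- **The primary endpoints.** A reader might infer that PASS, Quick-DASH MIC and GPE are also left unadjusted. The documents do not support this: the weights may leave a different diagnostic mix, but the outcome model then conditions on the group.

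**Conclusion.** The inconsistency is established from the text: a declared stratifier is missing from the propensity covariates and from the mixed models for five hierarchical outcomes. It is confined to key secondary endpoints, on which claims are made only if PASS, Quick-DASH MIC and GPE all succeed.

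The consequence is possible residual confounding by diagnosis, of unknown size. The scenario illustrations give roughly 0.5 to 2.5 points, and the crudest product reaches 4.5 at its most extreme assumed inputs. All are below the 10-point bound. They rest on assumed group shares, surgery rates, outcome gaps and proxy accuracy. A reader might infer that the equivalence reading would be overturned; nothing in the SAP shows that. The point is worth correcting before analysis because the remedy is simple and delivers the design that the SAP claims.

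**What to change.** 1. Add the four-level diagnostic group as a row in Box 1 and as a term in the propensity model.
2. Add the same factor to the fixed effects of every mixed model in Analysis methods, and to the continuous part of the Table 2 footnote, to match the logistic models.
3. Report the weighted standardised difference for diagnostic group beside the one already provided for in Table 1.

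Estimating weights separately within each diagnostic group is not advised. At 1:15, 992 patients give 992/16 = 62 surgical patients, or about 62/4 = 15 per group on average, against a long covariate list.

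The cost is SAP wording and three parameters (four levels minus one) per model. The variable is already in Table 1, so no new data are needed.
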